6.5.2. Concomitant Antihyperglycemia Medication

Patients treated with metformin in this study must be on a stable dose for at least 3 months prior to screening. The prescreening dose and formulation (short-acting or long-acting) must be maintained from the time of screening through the patient's last visit, except as required for rescue therapy (Section 6.1.2.3).

Dose adjustments of allowable OAM therapy are permitted after randomization (during the treatment period) under the following circumstances:

- in situations that require short-term treatment interruption in line with the product labeling for each respective country;
- in situations that require dose adjustment or discontinuation per country-specific label, for example, in the case of reduced eGFR;
- in the case of increased hypoglycemia risk during the treatment period (as described in Section 6.1.2.2).

Dose reduction of allowable OAM therapy during the trial should be properly documented.

In patients who require rescue therapy, dose increase of allowable OAM therapy is permitted, but the dose and the reason for change must be properly documented in the eCRF.

Guidance for treatment during the safety follow-up period is provided in Section 4.1.1.

6.5.3. Medications that Promote Weight Loss

Prescription or OTC medications that promote weight loss are exclusionary if used within the 3 months prior to screening, or any time after screening (see Section 6.5). If started after screening, these medications should be stopped immediately. In addition, patients should not receive an intensive diet/exercise program with the intent of reducing body weight at any time during the study, other than the lifestyle and dietary measures for diabetes treatment (see Section 5.3).

6.5.4. Systemic Glucocorticoids

Chronic systemic glucocorticoid therapy (excluding topical, intraocular, intranasal, or inhaled preparations) is exclusionary if used >14 consecutive days during the 1-month period before screening or between screening and randomization at Visit 3.

Patients treated with these medications after randomization will be excluded from the efficacy evaluable population for analyses if they receive:

- >14 days consecutive days of therapy, or
- More than one course of therapy during the study.

6.5.5. Antihypertensive Medications

If used, anti-hypertensive therapy should be kept stable throughout the trial to allow assessments of the effect of randomized therapies on blood pressure.

6.5.6. Dyslipidemia Medications

If used, dyslipidemia therapy should be kept stable throughout the trial to allow assessments of the effect of randomized therapies on lipid endpoints.

6.6. Dose Modification

Dosing will be individualized based on FG from SMBG. See Section 10.8 for details of dose modification.

6.7. Intervention after the End of the Study

After the end of the treatment period patients should continue to monitor their FG levels. The treating physician should then make the decision based on local clinical practice, if and what additional antihyperglycemic treatment needs to be administered.

Investigational product will not be made available to patients after conclusion of the study. After IP is discontinued, an appropriate diabetes treatment regimen will be initiated by the investigator.

6.7.1. Treatment after Study Completion

The last study treatment administration for patients treated with LY3209590 will be at Week 25 and for patients treated with insulin degludec the evening before the last study visit at Week 26. The washout of LY3209590 may take up to 10 weeks to complete. Any appropriate antihyperglycemic treatment must therefore be instituted slowly and under regular supervision of blood glucose profiles after discontinuation of LY3209590. If another basal insulin is used as a replacement for LY3209590 or insulin degludec, insulin therapy will be instituted using the Riddle algorithm as needed based on FG (Section 10.8). Since CCI

Therefore, a slow up-titration of another basal insulin is necessary to prevent hypoglycemia due to overlapping insulin action. For example, no insulin would be required until the study participant's blood glucose increases to >100 mg/dL, and then daily basal insulin would be initiated and adjusted based on FG.

Study participants assigned to the insulin degludec treatment group will switch to another glucose lowering regimen per investigator guidance after the last study treatment administration. If they switch to an insulin treatment and insulin degludec is chosen, they can continue with the same dose used until Visit 20 of the study. If they switch to another basal insulin (e.g., insulin glargine), study participants should inject a daily dose, which is 20% lower than the last dose of insulin degludec used before Visit 20 and titrate under supervision of the investigator using the country-specific label for their pre-study basal insulin.

7. Discontinuation of Study Intervention and Participant Discontinuation/Withdrawal

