Tertiary/Exploratory	

 To establish the equivalent dose of LY3209590 relative to insulin degludec 	
 Insulin dose at baseline and Week 26

 To investigate the safety and tolerability of LY3209590 compared with insulin degludec in study participants with T2DM 	
 Treatment-emergent adverse events Incidence and rate of hypoglycemia events during the post-treatment follow-up period Discontinuation of IP due to adverse events Clinical laboratory results Injection site reactions Liver aminotransferase change from baseline to Weeks 12 and 26 Triglyceride and FFA change from baseline to Weeks 12 and 26

Objectives	Endpoints
	
 • Body weight change from baseline at Weeks 12 and 26

 • To establish the relationships between dose/exposure and key safety and efficacy measures for LY3209590 	
 • LY3209590 exposure-response relationships for key efficacy and safety measures (e.g., glycemic control, hypoglycemia and safety labs).

 • To characterize the effects of LY3209590 on exploratory PD biomarkers 	
 • Lipids (cholesterol, LDL, HDL, triglycerides) • Biomarkers of lipolysis (FFA) • SMBG glucose profiles

 • To characterize Continuous Glucose Monitoring Parameters derived from FGM 	
 • Various parameters derived from FGM (for example average daily glucose, Time in target range 70 to 180 mg/dL, time in hyperglycemia, time in hypoglycemia)

 • To explore the development of LY3209590 ADAs 	
 • The frequency of antibody formation to LY3209590 and relationship to safety and efficacy markers will be determined.

 • To explore the compliance with the dosing regimen 	
 • Incidence and percentage of missed doses of LY3209590 and insulin degludec.

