10.8.2. Insulin Degludec

Insulin degludec will be administered at a starting dose of 10 Units. For subsequent dose adjustments, a dosing algorithm (adapted from Riddle et al. 2003) will be used by investigators

for initiating and adjusting insulin degludec to target an FG ≤ 100 mg/dL (< 5.6 mmol/L) for patients to achieve glycemic goal.

In situations where patient safety is a concern or where dose adjustments have not had the desired therapeutic effect, investigators may make increased or decreased adjustments to the dose of insulin degludec recommended by the dose-adjustment algorithm and have to document the clinical rationale for the deviation as well as inform Lilly Medical per email.

At the time of site visit or telephone visit, the investigator will assess the patient's glycemic control for the previous week and, if necessary, inform the patient about any needed dose adjustment. The dose will be based on the patient's blood glucose value. Adherence to the dosing algorithm provided for this study is mandatory from Visit 3 (randomization) up to Visit 20 (Week 26), inclusive. Dose increases may be made at weekly intervals and no sooner than 5 days following the last dose increase. In some cases, patient visits could occur sooner than 5 days apart due to the allowable visit window; however, there should be no dose increase if at least 5 days have not elapsed since the previous dose increase. In contrast, the insulin degludec dose may be reduced at any time on the judgment of the investigator. Any deviations from this guidance must be supported by clinical evidence and accompanied by information of Lilly Medical.

Insulin dose algorithms have been reviewed by Strange (2007). The insulin degludec dose increase algorithm is adapted from Riddle et al. 2003 and will be determined based on the definition of what is termed the "Algorithm FG." The Algorithm FG is the median of the FG (determined from SMBG) of Days 5, 6, and 7 since the last insulin dose increment. If the interval since the last dose adjustment has been longer than 7 days, the dose increase is determined by the median of the FG of the last 3 days. If the patient only measured their FG on 2 of the last 3 days, then the lesser of those 2 FG values should be used as the Algorithm FG. If only 1 FG measurement is available for the last 3 days, then the investigator should use his/her discretion in determining whether there should be a dose adjustment based on that single FG value.

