As it is desired to achieve glycemic goals in as many patients as possible, contingencies are provided to accommodate prespecified protocol visits and to increase the dose of insulin degludec in a timely manner. Therefore, if the last dose increment was 5 days previous, then the dose increment is determined by the Algorithm FG, which is the lesser of the 2 FG values from Day 4 and Day 5. If the dose increment was 6 days previous, then the Algorithm FG is the lesser of the 2 FG values from Day 5 and Day 6. In both of these cases, if only 1 of the 2 FG values is available, then the investigator should use his/her discretion in determining whether there should be a dose adjustment based on that single FG value.

The dose increase algorithm is defined as follows:

- If the Algorithm FG is 101 to 120 mg/dL (5.6 to 6.7 mmol/L), increase the dose by 2 U
- If the Algorithm FG is 121 to 140 mg/dL (6.8 to 7.8 mmol/L), increase the dose by 4 U
- If the Algorithm FG is 141 to 180 mg/dL (7.9 to 10.0 mmol/L), increase the dose by 6 U
- If the Algorithm FG is > 180 mg/dL (10.0 mmol/L), increase the dose by 8 U

The treat-to-target FG is ≤ 100 mg/dL (< 5.6 mmol/L). The insulin degludec dose will not be increased if any SMBG was documented at ≤ 70 mg/dL (< 3.9 mmol/L) at any time in the

preceding week. Dose decreases of 2 to 4 U per adjustment may be permitted if multiple episodes of hypoglycemia with SMBG ≤ 70 mg/dL (< 3.9 mmol/L) were recorded, if severe hypoglycemia (requiring assistance) occurred, or if any SMBG was documented at ≤ 54 mg/dL (≤ 3.0 mmol/L) in the preceding week.

[figure not shown]

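### Protocol Section 6.7.1 gives two unreconciled instructions for a degludec participant who changes to another basal insulin, and its label reference does not fit an insulin-naive trial

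*Protocol*

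**What the plan says.** Protocol Section 6.7.1 covers treatment after the last study dose. Its first paragraph deals mostly with LY3209590 washout, but one sentence names both arms: "If another basal insulin is used as a replacement for LY3209590 or insulin degludec, insulin therapy will be instituted using the Riddle algorithm". That sentence makes the insulin conditional on fasting glucose and refers to Section 10.8.

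The last paragraph is about the degludec group only. Participants who stay on degludec may keep their dose. For those who move to a different basal insulin, with glargine as the example, "study participants should inject a daily dose, which is 20% lower than the last dose of insulin degludec used before Visit 20". They are then to "titrate under supervision of the investigator using the country-specific label for their pre-study basal insulin".

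In Section 10.8.2, the place to which the first instruction leads, the opening sentence reads: "Insulin degludec will be administered at a starting dose of 10 Units". The section then presents its algorithm as one that investigators use "for initiating and adjusting insulin degludec to target an FG" of 100 mg/dL or below. The increments depend on fasting glucose and run from 2 to 8 U. The lowest rung is: "If the Algorithm FG is 101 to 120 mg/dL (5.6 to 6.7 mmol/L), increase the dose by 2 U".

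Section 3 of the protocol lists this among the tertiary/exploratory endpoints: "Incidence and rate of hypoglycemia events during the post-treatment follow-up period". SAP Section 5.10.3.2, Table BDCL.1, compares post-treatment hypoglycemia between arms up to Visit 801, using all data after study drug is stopped in the Safety Population.

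**The concern.** Consider a degludec completer who changes to another basal insulin at Visit 20. Both paragraphs of Section 6.7.1 describe this participant on the same day. One sends the site to the trial's titration algorithm. The other gives a percentage reduction and sends the site to a product label. Neither mentions the other, limits its own scope or says which prevails.

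The label reference has a further problem. It is the label of an insulin used before the study, in a trial of insulin-naive patients.

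What is at stake is first the consistency of insulin dosing during a transition between insulins. Second is the follow-up hypoglycemia comparison, where the degludec arm could carry differences between sites that come from the wording and not from the treatments.

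**Working it through.** The plan gives no figure to reproduce on this point. The check is a comparison of text, followed by simple arithmetic on one possible reading.

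**1. The two instructions side by side (Section 6.7.1)**

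| | First paragraph | Last paragraph |
|---|---|---|
| Who | Both arms, degludec named | Degludec arm only |
| When | Another basal insulin replaces study drug | Another basal insulin replaces study drug |
| Start | Not stated in the sentence; points to Section 10.8 | 0.8 × last degludec dose |
| Titration source | Fasting-glucose algorithm in Section 10.8 | Country-specific label |

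The last row differs whatever view is taken of the row above it. Suppose the 20% reduction sets the start and the algorithm governs only later steps. The last paragraph still names its own titration source, so two sources remain for one participant.

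**2. Does the label reference have a referent?** The trial is in insulin-naive patients (title; Section 9.1). Exclusion 26 bars insulin in the 3 months before screening, apart from acute use of at most 14 days within the last 6 months. The Section 6.5 table prohibits subcutaneous insulin during screening and lead-in, again apart from acute therapy. An ongoing basal regimen at entry is therefore not expected, and an instruction to titrate "using the country-specific label for their pre-study basal insulin" cannot be followed as written for the intended population.

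**3. Do the starting doses conflict?** This depends on the reading. The first paragraph speaks of instituting therapy by the algorithm, Section 10.8.2 describes the algorithm as serving initiation as well as adjustment, and the only start it gives is 10 units. On that reading the first paragraph implies 10 U and the last implies 0.8 × D, where D is the last degludec dose. The documents give no end-of-study dose, so D is an assumption and a range is shown.

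| Assumed D (U) | 0.8 × D (U) | Algorithm start (U) | Ratio |
|---|---|---|---|
| 10 | 8 | 10 | 0.8 |
| 12.5 | 10 | 10 | 1.0 |
| 20 | 16 | 10 | 1.6 |
| 40 | 32 | 10 | 3.2 |
| 60 | 48 | 10 | 4.8 |

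The starts are equal only where 0.8 × D = 10, that is D = 12.5 U. Below that the order reverses.

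**4. How long could a gap last, on the same reading?** The number of weekly increases needed to go from 10 U to 0.8 × D is (0.8 × D − 10) / step, rounded up.

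- Step 8 U: 6/8 = 0.75, 22/8 = 2.75 and 38/8 = 4.75, so 1, 3 and 5 weeks for D = 20, 40 and 60. This requires fasting glucose above 180 mg/dL at every step.
- Step 2 U: 6/2 = 3, 22/2 = 11 and 38/2 = 19 weeks.

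Follow-up lasts 5 weeks (Section 4.1), so at the higher assumed doses a gap could persist through much or all of it.

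**5. Which analyses are touched?** Section 6.7.1 governs treatment after Visit 20. The Week 26 HbA1c endpoint and the treatment-period hypoglycemia endpoints are outside its reach. The post-treatment hypoglycemia rows of Table BDCL.1 are within it, but only through degludec participants who change basal insulin.

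**The case against.** The best defence has four parts.

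- **The starting-dose conflict is inferred.** Section 10.8.2 states the 10-unit start in its own sentence, for degludec, and then introduces the algorithm for later adjustments. The increments themselves contain no start, and Section 6.7.1 never says to restart a treated participant at 10 U. This stands. A reader might infer that the protocol prescribes two starting doses up to 4.8-fold apart. The documents support that only on one reading and with an assumed last dose.
- **The specific paragraph would naturally prevail.** The last paragraph is about the degludec arm, and the first sits among remarks on LY3209590 washout, just before a redaction that might qualify it. This has some weight. But the sentence in question is complete before the redaction and names degludec expressly, and no precedence is stated.
- **Some participants may have used insulin before.** Exclusion 26 allows short acute use and does not itself bar insulin more than 3 months before screening. This stands. It would go too far to say that no participant can have such a history; the supported statement is that no ongoing basal regimen is expected.
- **The endpoint effect is small in scope.** The comparison is exploratory. Some degludec participants will stay on degludec or take non-insulin agents, and Sections 6.7 and 6.7.1 already leave the regimen to local judgement. This stands as a limit on the consequence. It does not remove the conflict: once another basal insulin is chosen, the protocol does give dosing instructions, and they disagree.

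**Conclusion.** The point holds as an internal contradiction in Section 6.7.1. The conflict in titration source, and the label reference with no evident referent, rest on the text alone and need no assumption. The starting-dose conflict is conditional: it requires the first paragraph to import the 10-unit start, and its size (8 to 48 U against 10 U for last doses of 10 to 60 U) rests on assumed doses.

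The practical consequence is that two sites, each following the protocol, could dose similar participants differently during a change of insulin. Statistically, this is one avoidable source of variation among several in an exploratory follow-up comparison. Its size cannot be computed from the documents. A reader might infer that the follow-up hypoglycemia comparison is biased, or that the main efficacy and safety results are compromised. The documents support neither: no direction of effect can be derived, and Week 26 HbA1c and treatment-period hypoglycemia are not affected. It should be corrected, chiefly on safety grounds.

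**What to change.** Reconcile the two paragraphs of Section 6.7.1 so that a single instruction, covering both the start and the titration source, governs a degludec participant who moves to a different basal insulin. If both paragraphs are kept, state the scope of each and which takes precedence. Correct the reference to a basal insulin used before the study so that it points to something a participant in this trial will have. If Section 10.8 remains the reference, say whether its starting dose is meant to apply here or only its adjustment steps. Which rule applies is for the sponsor's medical team to decide.

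The cost is a wording change in one protocol section and a memo to sites. No visits, data items or analyses are added.

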7.1. Discontinuation of Study Intervention

Study drug may be permanently discontinued or temporarily withheld during the study.

Participants who permanently discontinue study drug early will undergo early termination procedures, which include

- an ET visit or,
- post-treatment follow-up visits (ED1, ED2) (Section 4.1.1).

The investigator will complete any AE reporting and necessary follow-up.

7.1.1. Permanent Discontinuation from Study Treatment

Possible reasons leading to permanent discontinuation of investigational product include, but are not limited to:

- **Participant decision**
 - the patient or the patient's designee, for example, parents or legal guardian requests to discontinue IP.
- **Hepatic event or liver test abnormality:** Participants who are discontinued from IP due to a hepatic event or liver test abnormality should have additional hepatic safety data collected via eCRF

Discontinuation of the IP for abnormal liver tests **should be** considered by the investigator when a participant meets one of the following conditions after consultation with the sponsor-designated medical monitor:

- ALT or AST >8X ULN
- ALT or AST >5X ULN for more than 2 weeks
- ALT or AST >3X ULN and total bilirubin level (TBL) >2X ULN or international normalized ratio (INR) >1.5
- ALT or AST >3X ULN with the appearance of fatigue, nausea, vomiting, right upper-quadrant pain or tenderness, fever, rash, and/or eosinophilia (>5%)
- alkaline phosphatase (ALP) >3X ULN
- ALP >2.5X ULN and TBL >2X ULN
- ALP >2.5X ULN with the appearance of fatigue, nausea, vomiting, right quadrant pain or tenderness, fever, rash, and/or eosinophilia (>5%)

In addition, participants will be discontinued from the IP in the following circumstances:

- if a patient is inadvertently enrolled and it is determined that continued treatment with IP would not be medically appropriate (see Section 7.2.1)

- if a patient is diagnosed with an active or untreated malignancy (other than basal or squamous cell skin cancer, in situ carcinomas of the cervix, or in situ prostate cancer) after randomization
- if the investigator or sponsor decides that the patient should be withdrawn from IP; if the investigator decides to permanently discontinue IP because of an SAE or a clinically significant laboratory value, Lilly or its designee should be alerted immediately
- if the investigator, after consultation with Lilly Medical, determines that a systemic hypersensitivity reaction has occurred related to study drug administration, the participant should be permanently discontinued from IP.

See the Schedule of Activities for data to be collected at the time of intervention discontinuation and follow-up and for any further evaluations that need to be completed.

Patients who stop the IP permanently may receive another glucose-lowering intervention, if appropriate, and will continue participating in the trial according to the protocol to collect all planned efficacy and safety measurements.

7.1.2. Temporary Discontinuation

In certain situations after randomization, the investigator may need to temporarily discontinue (interrupt) IP (for example, due to an AE or a clinically significant laboratory value). The maximum time allowed for a temporary interruption of IP is 14 days. If IP interruption is due to an AE, the event is to be documented and followed according to the procedures in Section 8.3 of this protocol. Investigators should inform the sponsor that IP has been temporarily interrupted. Every effort should be made by the investigator to maintain patients on IP and to restart IP after any temporary interruption, as soon as it is safe to do so. The data related to temporary interruption of IP will be documented in source documents and entered in the eCRF.

7.2. Participant Discontinuation/Withdrawal from the Study

A participant will be discontinued (withdrawn) from the study in the following circumstances:

- if he or she is diagnosed with any type of diabetes mellitus other than T2DM
- at any time at his/her own request
- at the discretion of the investigator for safety, behavioral, compliance, or administrative reasons
- if the participant becomes pregnant during the study
- if enrollment in any other clinical study involving an IP or enrollment in any other type of medical research judged not to be scientifically or medically compatible with this study
- participation in the study needs to be stopped for medical, safety, regulatory, or other reasons consistent with applicable laws, regulations, and good clinical practice (GCP)
- investigator decision
 - the investigator decides that the participant should be discontinued from the study

- if the participant, for any reason, requires treatment with another therapeutic agent that has been demonstrated to be effective for treatment of the study indication, discontinuation from the study occurs prior to introduction of the new agent
- participant decision:
 - the patient or the patient's designee, for example, parents or legal guardian requests to be withdrawn from the study.

Discontinuation is expected to be uncommon.

At the time of discontinuing from the study, if possible, an early discontinuation visit should be conducted, as shown in the Schedule of Activities (Section 1.3). See Schedule of Activities for data to be collected at the time of study discontinuation and follow-up and for any further evaluations that need to be completed. The participant will be permanently discontinued both from the study intervention and from the study at that time.

If the participant withdraws consent for disclosure of future information, the sponsor may retain and continue to use any data collected before such a withdrawal of consent. If a participant withdraws from the study, he/she may request destruction of any samples taken and not tested, and the investigator must document this in the site study records.

